## 2. Glossary and Abbreviations

BC	Breast cancer
DCIS	Ductal carcinoma in situ
IOUS	Intraoperative ultrasound
MRI	Magnetic resonance imaging
RCT	Randomized controlled trial
RFID	Radiofrequency identification
ROLL	Radioguided occult lesion localization
RRL	Radar reflector-localization
RSL	Radioactive seed localization
WGL	Wire-guided localization

### 3. Rationale

In the last decades, the proportion of breast cancer (BC) patients receiving breast-conserving surgery has increased steadily, reaching 70-80% in developed countries [1-3]. Since positive resection margins are strongly associated with local recurrence risk, the goal of breast surgery is the complete tumor removal and most national and international guidelines recommend re-operation, either in form of re-excision or mastectomy, until clear margins have been reached [4]. Re-operation rates vary widely, with population-based studies reporting a range of 15-35%, and the necessity for a second surgery can lead to increased patient anxiety, a delay in start of adjuvant treatment, worse cosmetic outcome and increased complication rates and costs [1,5-9]. Therefore, re-operation rate has been included as a quality indicator in several countries [10].

Several imaging-guided techniques have been developed to guide removal of non-palpable breast lesions, the oldest one being preoperative wire placement under ultrasound or mammographic guidance, usually followed by radiography or ultrasound of removed tissue [11]. Newer techniques, such as intraoperative ultrasound (IOUS), radioguided occult lesion localization (ROLL), radioactive seed localization (RSL), radar reflector-localization (RRL), magnetic localization, and radiofrequency identification (RFID) tags have been introduced as an alternative to wire-guided localization (WGL) [12,13].

To date, comparative data on the rates of successful lesion removal, negative margins and re-operations in patients undergoing different localization techniques are limited. In case of RSL and ROLL, several randomized controlled trials (RCTs) have been conducted, usually comparing these methods to WGL [11]. Regarding IOUS, results from three RCTs with WGL as control arm are available [14-16]. For the other markers that require a special probe to guide intraoperative detection, i.e., magnetic markers, radar reflectors and RFIDs, only data from prospective and retrospective cohort studies are available, which makes a direct comparison between different techniques challenging [17-20]. Further, since some of these studies were funded by the manufacturer of the marker examined, a potential bias cannot be excluded. In the vast majority of the available studies, the patient's perspective with regard to discomfort and pain level has not been evaluated.

The aim of the proposed study is to comparatively evaluate different imaging-guided localization methods used for surgical removal of non-palpable malignant breast lesions with regard to oncological safety and patient-reported outcomes.

## 4. Methods

### 4.1. Study design

Non-interventional observational international prospective cohort study

Investigator-initiated study

### 4.2. Aims and objectives

#### Primary outcomes:

- Intended target lesion and/or marker removal, independent of margin status on final histopathology
- Negative resection margin rates (defined as lesion removal with no invasive or non-invasive carcinoma on ink) at first surgery

#### Secondary outcomes:

- Rates of second surgery
- Rates of secondary mastectomy
- Resection Ratio, defined as actual resection volume divided by the calculated optimum specimen volume
- Duration of surgery in BC patients, defined as time between first incision and end of skin closure (patients receiving simultaneous reconstructive, oncoplastic or contralateral surgery will be excluded from this analysis)
- Marker dislocation rates
- Rates of marker placement failure, i.e., marker dislocation requiring a placement of a second marker
- Rates of localization failure, i.e., failed removal of marker or lesion, or necessity to switch to another intraoperative localization method
- Comparison of patient-reported outcomes (e.g., patient's discomfort, pain level, and impairment of breathing)
- Comparison of diagnostician/radiologist's satisfaction with marking technique
- Comparison of surgeon's satisfaction with localization technique
- Rates of "lost markers" (defined as markers placed prior to surgery and not retrieved at surgery)

- Volume and weight of resected tissue
- Impact of experience of study sites on other outcome measures, depending on the localization technique used
- Impact of self-reported ethnicity on other outcome measures
- Evaluation of surgical standards of care in different countries
- Evaluation of economic resources required for different localization techniques (material costs, operative time etc.)
- Evaluation of MRI artifacts
- Evaluation of complication rates related to marker placement
- Evaluation of perioperative complication rates

### **4.3. Inclusion and exclusion criteria**

#### Inclusion criteria

- Signed informed consent form
- Malignant breast lesion requiring breast-conserving surgery and imaging-guided localization (either DCIS or invasive breast cancer; multiple or bilateral lesions and the use of neoadjuvant chemotherapy are allowed)
- Planned surgical removal of the lesion using one or more of the following imaging-guided localization techniques:
  - o Wire-guided localization
  - o Intraoperative ultrasound
  - o Magnetic localization
  - o Radioactive seed localization
  - o Radioguided Occult Lesion Localization (ROLL)
  - o Radar localization
  - o Radiofrequency identification (RFID) tag localization
  - o Ink/carbon localization
- Female / male patients  $\geq$  18 years old

#### Exclusion criteria

- Patients not suitable for surgical treatment
- Patients requiring mastectomy as first surgery
- Surgical removal without imaging-guided localization

#### **4.4. Registration and therapy**

All patients with invasive or in situ breast cancer scheduled for a breast-conserving surgery and requiring imaging-guided localization should be informed about the possible participation in the MELODY study. The inclusion and exclusion criteria are verified by the investigator and written informed consent is obtained from the patient.

Surgical treatment, pathological assessment and postoperative locoregional and systemic therapy should be conducted according to institutional and national standards. Since the MELODY study is a non-interventional trial, the Study Sites do not deviate from their own institutional protocol at any timepoint.

Diagnostician/radiologist's and Surgeon's satisfaction with the marking and localization technique used are assessed using a short questionnaire.

Patient-reported outcomes are reported using a short questionnaire (to be completed between localization/surgery and postoperative visit).

Patients will be followed for 30 days postoperatively for perioperative complications. No long-term surveillance is required.

#### **4.5. Quality assurance**

To ensure consistent quality in localization and excision, the Study Site must have completed a minimum of 5 excisions using the localization device/method before enrolling patients in the respective cohort.

[figure not shown]
#### **4.6. Target accrual**

7416 patients

#### **4.7. Study duration**

2 years

**Study flow chart**

## 5. Data management

This part of the Protocol will discuss the Data Sharing and Data Management policy between two parties: The Provider & The Recipient. The Provider as per this agreement will be the Study Site supplying the dataset in accordance with the Protocol of the study. The Recipient will be the EUBREAST Study Group who will collect the data in accordance with the Data Protection policy as set out in this agreement. Study data will be collected and managed using REDCap (Research Electronic Data Capture) electronic data capture tools hosted at the server belonging to and managed by EUBREAST.

To register for the study, Study Sites (Providers) will contact the Head of their National Steering Committee to request participation in the Study and access to the online database. Each Study Site will then be designated a Site ID in format: Two-letter Country Code – Site number (e.g., DE-001 for the first German Study Site), which will be used as a prefix for the Patient ID (e.g., DE-001-001 for the first patient recruited at Study Site DE-001). All patients who consent to participation in the Study are recorded in the Subject Identification Log that remains at the study site. This document is the only record containing patient personal data and the corresponding Patient ID. EUBREAST does not have access to the Subject Identification Log at any time. No personal data will be disclosed under the Data Sharing Agreement. No patient identifiable data will be recorded for the purpose of the Study.

For further analysis data are filled in the REDCap-based eCRF by the Study Site. The printed version of CRF (PDF file) is also available. Its use is optional. All data are checked for plausibility through remote monitoring. The Monitors do not have access to patient data and do not visit Study Sites. Are the data insufficient for evaluation of predefined study aims, the Monitor will generate a query and Study Site will be requested to clarify.

REDCap has been disseminated for local use by more than 1,005 academic/non-profit consortium partners in 79 countries. Vanderbilt leads the REDCap Consortium, which currently supports more than 99,000 projects and 128,000 users. More information about the consortium and system security can be found at <http://www.projectredcap.org/>. REDCap is a secure, web-based application designed to support data capture for research studies, providing 1) an intuitive interface for validated data entry; 2) audit trails for tracking data manipulation and export procedures; 3) automated export procedures for seamless data downloads to common statistical packages; and 4) procedures for importing data from external sources.

REDCap is created by Vanderbilt University, with the server hosted by the EUBREAST. REDCap was developed specifically around HIPAA-Security guidelines. Web browser communication to the server is SSL-encrypted by default. All other ports are firewall protected.

Data is stored in MySQL databases on a separate server. This server is behind a firewall and can only be accessed from the IP address of the web server. An SSL-tunnel encrypts communication between the web and databases servers. File upload is secured between servers using the WebDAV protocol with SSL. “At rest” encryption is in place on the database server (aes-xts-plain64:sha256 with 512-bit keys). Daily back-ups are made of both servers and stored for two weeks prior to being deleted. Operating security updates are installed automatically. Antivirus software runs to a scheduled protocol on the web server. User passwords are managed directly. Accounts are disabled after 5 failed login attempts. Users are auto logged out after 30 mins of no activity. Daily audit tracking of users is in place with removal of unused user accounts.

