### **6.2. Acknowledged collaborators**

Collaborators will have made a considerable contribution to the study but will not have met the ICMJE criteria for authorship (non-author contributors). These will include:

- Heads of National Steering Committees representing countries without top recruiter status
- Members of National Steering Committees
- Local PIs of active Study Sites who have recruited at least ten study participants. Recruitment in this context includes submission of at least 10 completed data sets.

All acknowledged collaborators will be listed as MELODY Study Group.

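### The protocol provides for no comparison of consented with entered patients, so failures that are never submitted could go undetected, and Endpoint A turns on a few failures

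*Protocol*

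**What the plan says.** Protocol section 5 (Data management) describes how a patient gets from consent to the database:

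- **List of consented patients.** "All patients who consent to participation in the Study are recorded in the Subject Identification Log that remains at the study site". On central access: "EUBREAST does not have access to the Subject Identification Log at any time".
- **Role of the log.** "This document is the only record containing patient personal data and the corresponding Patient ID".
- **Numbering.** The Patient ID is the site prefix plus a number; the example is "DE-001-001 for the first patient recruited at Study Site DE-001".
- **Data entry.** "For further analysis data are filled in the REDCap-based eCRF by the Study Site". No time point relative to localization or surgery is given.
- **Monitoring.** "All data are checked for plausibility through remote monitoring", and "The Monitors do not have access to patient data and do not visit Study Sites". A query is raised when data are insufficient for the study aims.

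Section 4.4 (Registration and therapy) covers the eligibility check and written consent but no database registration step. The readable text contains no count of consented patients and no check of that count against the database.

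**The concern.** A plausibility check examines records that exist. It cannot detect a patient who consented, had a failed localization and was never entered. The only list of consented patients that the protocol describes is closed to the coordinating group, and no record has to exist before the outcome is known. Under the stated rules, the centre has no defined way to tell a complete cohort from one that lacks some of its failures.

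Endpoint A is exposed because failures are rare and the margin is a small absolute difference. Localization-failure and lost-marker rates, which section 8 names as the focus of the safety evaluation, are exposed in the same way, although they are secondary and exploratory.

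**Working it through.** **Inputs (protocol section 7.1).** WGL failure rate 0.6%; margin 1.1 percentage points; 1854 WGL and 927 patients per experimental group; alpha 0.417% (5%/12) per comparison. Sidedness is not stated. The shares of unsubmitted failures used below are assumptions.

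**Reproducing the plan.** Power = Φ(margin/SE − z), with SE = √[p(1−p)(1/927 + 1/1854)] and z = 2.638 (one-sided 5%/12).

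- Endpoint B: SE = √[0.85 × 0.15 × (1/927 + 1/1854)] = 0.01436; Φ(0.05/0.01436 − 2.638) = 80.03%. With alpha rounded to 0.00417 it is 80.04%, the stated figure.
- Endpoint A: SE = 0.003107; Φ(0.011/0.003107 − 2.638) = 81.7%, against the stated 80%.
- Two-sided alpha gives 73.1% (B) and 75.0% (A), so the plan's figures correspond to one-sided alpha.
- Total: 1854 + 6 × 927 = 7416, as in section 4.6.

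**Expected Endpoint A failures.** WGL: 1854 × 0.006 = 11.1. A device equal to WGL: 927 × 0.006 = 5.6. A device at the margin: 927 × 0.017 = 15.8.

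**How few failures decide the result.** Unweighted Wald upper bound for the difference in failure rates, with WGL at 11/1854 = 0.593%:

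| Device failures in 927 | Difference | SE | Upper bound | Result against 1.1% |
|---|---|---|---|---|
| 7 | 0.162% | 0.336% | 0.162 + 2.638 × 0.336 = 1.05% | pass |
| 8 | 0.270% | 0.352% | 0.270 + 2.638 × 0.352 = 1.20% | fail |

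With 8, 9 or 10 true failures, leaving out 1, 2 or 3 of them turns a fail into a pass.

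**Effect on the false-pass rate.** Take a device truly at the margin (1.7% against 0.6%). If a share d of failures is not submitted, the recorded failure rate is f(1−d)/(1−fd). The false-pass rate is Φ((0.011 − recorded difference)/SE − 2.638), with the entered group sizes kept at 927 and 1854.

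Example, d = 25% in both groups:

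- device: 0.01275/0.99575 = 1.280%
- WGL: 0.0045/0.9985 = 0.451%
- difference 0.830%, SE 0.401%
- Φ((1.100 − 0.830)/0.401 − 2.638) = Φ(−1.96) = 2.5%

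| Assumed share not submitted | Both groups, normal approximation | Both groups, exact enumeration of the Wald rule | Experimental group only, normal (exact) | WGL only, normal |
|---|---|---|---|---|
| 0% | 0.4% | 1.3% | 0.4% (1.3%) | 0.4% |
| 10% | 0.8% | 2.5% | 1.2% (3.1%) | 0.28% |
| 25% | 2.5% | 6% | 5.3% (9.9%) | 0.15% |
| 50% | 16% | 24% | 40.4% (44.5%) | 0.05% |

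Equal omission in both groups does not cancel. The margin is an absolute difference, and removing the same share of failures from both groups shrinks that difference.

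**The case against.** The strongest reply is that the protocol is silent here and states nothing wrong. Keeping an identifying log at the site is ordinary pseudonymisation, and a monitoring or data-management plan could ask for counts. The first part stands: local storage is not the fault, and the fix leaves it alone. The second part does not settle the matter. When a record is opened and how the denominator is fixed are data-collection rules, and no later analysis can recover a patient who was never entered.

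Several stronger readings are tempting, and the text does not support them:

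- **That the log is the only record made at consent.** Section 5 calls it the only record linking personal data to the Patient ID. A signed consent form also exists.
- **That reconciliation is ruled out, or that omission leaves no trace.** No sentence says so, and the flow chart is not visible. The ID example suggests numbering by order of recruitment, so gaps could show if IDs are assigned at consent and checked; neither is stated. REDCap audit trails may show late entry.
- **That the authorship rule rewards withholding failures.** Section 6.2 says "Recruitment in this context includes submission of at least 10 completed data sets". A completed record of a failed localization counts the same as a success.
- **That every lost marker drops out of Endpoint A.** The endpoint is removal of the target lesion and/or the marker, so a lost marker with the lesion removed can still be a success.
- **That the bias must favour the newer technique.** If only WGL failures are withheld, the false-pass rate falls below 0.4%.

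The size is also uncertain. The shares are assumed, and with about 16 and 11 expected events the normal approximation is rough. A score test in place of the Wald bound gives lower figures for experimental-only omission: 0.2%, 2.3% and 18% at 0%, 25% and 50%.

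**Conclusion.** The concern holds as a gap in data collection. It is not evidence of bias. As written, patients could go unsubmitted after a failed localization without the coordinating group having a defined means of noticing, and one to three such patients can decide an Endpoint A comparison.

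For a device at the margin, with the same share of failures missing in both groups, the false-pass rate rises from 0.4% to about 0.8%, 2.5% or 16% at assumed shares of 10%, 25% and 50% (exact: from 1.3% to 2.5%, 6% or 24%). It is higher if only experimental-group failures are missing and lower than 0.4% if only WGL failures are. These figures rest on one-sided alpha, an unweighted Wald bound, the plan's own failure rates and shares for which the protocol gives no source. They show sensitivity and do not predict what will happen. The change is worth making because it is cheap and a time-stamp made before surgery cannot be created afterwards.

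**What to change.** In sections 4.4 and 5:

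1. Require the site to open a time-stamped REDCap record at consent and before localization or surgery, holding Patient ID, date and planned technique and no personal data.
2. Have each site report its number of consented patients by planned technique and explain any missing IDs. The identifying log stays at the site.
3. Use all pre-registered patients as the reported denominator and give the number without outcome data by technique.
4. Add a sensitivity analysis over a range of assumed failure rates for those patients, for example a tipping-point analysis. Do not count them all as failures: a device equal to WGL expects 5.6 failures and fails at 8, so with WGL left at 11, about three missing records (3/927 = 0.3%) would sink it.

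Cost: two or three protocol sentences, one three-field form and one aggregate count per site. Sites enter one short form earlier, and observed failure rates may rise slightly.

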### **5.1. Data Purpose**

The Recipient will have access to the Data Set to the extent necessary for the purpose of the Study. The pseudonymized Data Set shall be made available only to the Party responsible for Statistical Analysis. The Data Set will not be disclosed, transferred, or made available to any other third party. Summary Safety data may be transferred to the Manufacturers; however, this will NOT include any personal patient data. The Data Set will be kept confidential, and all reasonable steps will be taken to protect it against accidental or unlawful loss, modification or destruction, or unauthorized access, disclosure, copying, use, misappropriation, or modification. Following study closure, datasets cannot be transferred to any third party without the permission of the Recipient.

The results will be published in an academic publication. The Study Sites will be informed about the publication, and the publications will be uploaded to the EUBREAST and iBRA-NET websites, the link to this publication will be sent to Study Sites. In accordance with customary scientific practice, any publications or presentations made in relation to the results, whether in oral, visual, or written form, the Study Site will be acknowledged as the source of the Data Set (see section “Publication and authorship policy”).

### **5.2. Data Ownership**

The data is submitted by the Provider with the intention of contributing to a combined dataset. Providers can access their Study Site’s complete dataset at any point within the study recruitment period.

## **6. Publication and authorship policy**

All presentations and publications will be made on behalf of the EUBREAST and iBRA-NET Study Groups. Two levels of authorship are proposed based on degree of study participation:

### **6.1. Named authors**

Named authors will be required to meet the International Committee of Medical Journal Editors (ICMJE) criteria ([www.icmje.org](http://www.icmje.org)) for authorship. These will include:

- Principal Investigator and Deputy Principal Investigator
- Members of the International Steering Board
- Heads of National Steering Committees representing countries with top recruiter status
- Main statistician

### **6.2. Acknowledged collaborators**

Collaborators will have made a considerable contribution to the study but will not have met the ICMJE criteria for authorship (non-author contributors). These will include:

- Heads of National Steering Committees representing countries without top recruiter status
- Members of National Steering Committees
- Local PIs of active Study Sites who have recruited at least ten study participants. Recruitment in this context includes submission of at least 10 completed data sets.

All acknowledged collaborators will be listed as MELODY Study Group.

## 7. Statistical considerations

### 7.1. Sample size consideration

This prospective non-interventional study is designed to evaluate and compare the performance of 6 imaging-guided techniques with wire-guided localization (WGL). It is hypothesized that the imaging-guided methods perform better or equal to WGL in terms of the likelihood of the intended lesion removal, as well as the likelihood of a negative margin. Each localization device/method will be compared to the wire-guided localization considered standard using propensity scoring. The first co-primary endpoint is the intended lesion removal. The failure rate of WGL in the literature is 0.6%, giving an identification rate of 99.4% [11]. A difference of 1.1% between techniques is considered to be clinically significant. Given an allocation rate of 2:1 for WGL : experimental group, sample sizes of 1854 in the WGL group and 927 in each experimental group are sufficient to restrict the upper boundary of the respective confidence interval for the differences in identification rates of WGL versus experimental device to 1.1% with a power of 80%. The other co-primary endpoint is the positive margin rate. The positive margin rate of WGL in the literature is 15%, yielding a negative margin rate of 85%, respectively [21]. A clinically significant difference between techniques was considered to be less than 5%. Assuming that each experimental method also has a negative margin rate of 85%, the upper limit of the confidence interval for the difference in negative margin rates is limited to 5% with a power of 80.04%. Each commercially available device will be analyzed in a separate cohort. To adjust for multiplicity and to keep an overall type 1 error of 5%, each of the 12 comparisons are planned with an alpha of 0.417%.

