### **Endpoint B**

Rate of negative resection margin rates (defined as lesion removal with no invasive or non-invasive carcinoma on ink) at first surgery, to be compared between imaging-guided techniques and WGL.

Hypotheses:

H20:  $P2_{\text{exp}_i} - P2_{\text{WGL}} \leq -0.05$  versus

H21:  $P2_{\text{exp}_i} - P2_{\text{WGL}} > -0.05$ ,

with  $P2_{\text{exp}_i}$ ,  $P2_{\text{WGL}}$  being the negative resection margin rates in the  $i$ th experimental group and in WGL group.

To balance the baseline variables between treatment groups, inverse-probability-of-treatment-weighting (IPTW) is applied to each pairwise comparison. Variables used for balancing include those variables that are associated with the outcome. The IPT weights will be considered for all primary endpoint comparisons.

Analysis of the primary endpoints:

The difference of the rates between the groups (WGL – experimental group  $i$ ) will be calculated and compared to the respective margin. The null hypothesis is rejected, if the lower bound of a defined confidence interval increases the margin.

To define the width of each confidence interval, the Holm-Bonferroni method will be applied:

1. Step: t-tests between each experimental method and WGL will be applied.
2. Step: The hypotheses are ordered by their nominal p-values. Only hypotheses indicating that the effectiveness of imaging-guided technique exceeds WGL are considered here. If none of the hypotheses shows this trend, the hypotheses are ordered by the lower bound of the 95% confidence interval of the estimated beta, starting with the highest number.
3. Step: For the first hypothesis in this order, a  $(100\% - \frac{5\%}{12})$ -confidence interval will be calculated. If the lower bound of this confidence interval increases the respective margin, the null hypothesis is rejected, and the next step will be applied. If the lower bound of this confidence interval does not increase the respective margin, the null hypothesis is accepted, and the procedure ends here.

4. Step: For the next hypothesis in this order, a  $(100\% - \frac{5\%}{11})$ -confidence interval will be calculated, and decisions are made as in the previous step. In each following step, the confidence interval gets incrementally larger, by dividing 5% through the number of untested hypotheses.

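### Endpoint A's stated 80% power rests on a large-sample approximation with about six expected failures per technique; it cannot hold together with the stated 5% family-wise error

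*Protocol*

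**What the plan says.** Section 7.1 of the Protocol sets out the Endpoint A calculation. The control rate is taken from the literature: "The failure rate of WGL in the literature is 0.6%, giving an identification rate of 99.4"%. The margin is 1.1 percentage points ("A difference of 1.1% between techniques is considered to be clinically significant"), and allocation is 2:1. The text calls 1854 WGL and 927 patients per technique "sufficient to restrict the upper boundary of the respective confidence interval for the differences in identification rates of WGL versus experimental device to 1.1" percentage points, at 80% power. Alpha is 0.417% for each of 12 comparisons, that is 5%/12, to keep the overall type 1 error at 5%.

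For Endpoint B the section states outright that the experimental rate is assumed equal to WGL, and gives 80.04% power. For Endpoint A it gives no experimental rate. It offers only the general hypothesis that "imaging-guided methods perform better or equal to WGL in terms of the likelihood of the intended lesion removal".

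Section 7.2 repeats the 5% family-wise claim under a Holm-Bonferroni procedure. Its Step 1 says "t-tests between each experimental method and WGL will be applied". Those tests serve to order the hypotheses. Rejection in Steps 3 and 4 rests on a confidence interval whose type is not named. Inverse-probability-of-treatment weights apply to all primary comparisons.

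**The concern.** With so few failures, a normal approximation for a rate difference is poor, and it is worst far out in the tail, where a 0.417% alpha sits. A sample that shows few failures by chance has both a small observed difference and a small estimated standard error, so a Wald-type bound falls inside the margin too easily.

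Endpoint A is co-primary and asks whether the target was removed at all. At the margin, an experimental technique fails in 1.7% of cases against 0.6% for WGL, nearly three times as often. If the interval is too short, such a technique is declared non-inferior more often than planned. If the interval is sound, the stated power is not delivered, and techniques equal to WGL may fail to show it.

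**Working it through.** **Inputs (section 7.1).** WGL failure rate 0.006; margin 0.011; n = 1854 WGL and 927 experimental; alpha 0.05/12 = 0.00417, z = 2.638. Assumption: experimental failure rate also 0.006. Sidedness is not stated; one-sided use reproduces the plan's figures.

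**Reproducing the plan.** Unpooled normal formula: power = Φ(margin/SE − z), SE = √[p(1−p)(1/1854 + 1/927)].

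- Endpoint B: SE = √[0.85 × 0.15 × (1/1854 + 1/927)] = 0.01436; 0.05/0.01436 − 2.638 = 0.843; power 80.0% (stated 80.04%).
- Endpoint A: SE = √[0.994 × 0.006 × (1/1854 + 1/927)] = 0.003107; 0.011/0.003107 − 2.638 = 0.903; power 81.7% (stated 80%).

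B therefore drives the sample size. For A, a noncentral t gives 81.6% and is also a large-sample method. The alternatives do not reproduce A: two-sided 0.417% gives 75.0%, continuity correction 74.0%, and asymptotic Farrington-Manning 43.6%.

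**Expected failures.** 927 × 0.006 = 5.6 and 1854 × 0.006 = 11.1.

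**Exact check.** Rejection probabilities were summed over all pairs of binomial counts at 1854/927, one-sided 0.417%. Size is taken at failure rates 1.7% vs 0.6%, power at 0.6% vs 0.6%.

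| Method | True size | Power |
|---|---|---|
| Wald (normal) | 1.35% | 77.3% |
| Farrington-Manning / Miettinen-Nurminen score | 0.20% | 46.1% |
| Newcombe | 0.18% | 44.9% |
| Exact unconditional, score ordering | at most 0.417% | about 52% |
| Score, calibrated at 0.6% control rate | 0.417% | 56.7% |
| Wald, calibrated at 0.6% control rate | 0.417% | 60.8% |
| Likelihood ratio | 0.46% | 60.5% |

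The Wald ratio is 1.35/0.417 = 3.2.

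**One outcome by hand.** Take 11 WGL failures and 7 experimental failures. The difference is 7/927 − 11/1854 = 0.00162. The Wald SE is √[0.00755 × 0.99245/927 + 0.00593 × 0.99407/1854] = 0.00336, and (0.011 − 0.00162)/0.00336 = 2.79, above 2.638: non-inferior. The score statistic for the same data is 2.14: not shown. With 11 WGL failures, Wald accepts up to 7 experimental failures, the likelihood ratio 6, and score and Newcombe 5. The choice of interval thus decides the result at the counts the plan expects.

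**Family-wise consequence if Wald is used.** With all Endpoint A nulls at the boundary, the six first-step errors sum to 6 × 1.35% = 8.1%, against a share of 6 × 0.417% = 2.5%.

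**Sensitivity.**

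- Better experimental rate: at 0.4% failures, score power is 76% and likelihood-ratio power 87%; at 0.3%, 88% and 95%.
- Later Holm steps: score power is 62% at 5%/6 and 75% at 5%/3; the Wald error ratio is 2.5 and 1.9.
- If the section 7.2 interval is two-sided (tail 0.208%): score power is 32%, and the Wald error is 4.2 times its nominal tail.

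**The case against.** The strongest reply is that the criticised interval is not in the document. Section 7.2 names no interval type, its t-tests only order the hypotheses, and the interval may properly be fixed in a statistical analysis plan that is not shown. That stands. A reader might infer that the protocol prescribes a normal interval and so already carries a threefold error and a family-wise error well above 5%. The text does not support this: the inflation depends on a normal or t-based interval being chosen. What section 7.1 does fix is the 80%, and a sound interval chosen later makes that figure wrong.

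Three further replies stand in part.

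- There is no slip of arithmetic. The stated figures reproduce; it is the approximation that is inadequate.
- Equal 99.4% rates are an assumption for Endpoint A. It is the natural reading and it reproduces the figure, but power is sensitive to it, so a range belongs beside it.
- The enumeration is unweighted and at the first Holm step. It does not give the operating characteristics of the weighted estimator. Weighting would usually reduce the effective sample size further; that was not modelled.

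Part of the gap at 45-46% is conservatism, since score and Newcombe run at about half the nominal level. Tests calibrated at a 0.6% control rate recover 57-61%, but that calibration is not guaranteed at other control rates.

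**Conclusion.** The point holds in this form: at 1854/927, with 99.4% in both groups, no method examined gives Endpoint A both 80% power and the 0.417% error on which the 5% family-wise claim rests. A Wald interval comes near the power (77%) at 3.2 times the error. Methods that hold the level give about 45-60%, a shortfall of roughly 20 to 35 points; those that hold it across control rates give about 45-52%.

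This rests on one-sided alpha, equal failure rates of 0.6%, no weighting, and the first Holm step. That the plan used a normal-type formula is inferred, but firmly, because the same formula also returns Endpoint B's figure. Endpoint B's power is not in question. Nor does it follow that the trial must be enlarged: about 1500 per technique and 3000 WGL would be needed for 80% score power, but stating the lower power honestly is a legitimate alternative.

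**What to change.** **Section 7.1.** State the experimental rate assumed for Endpoint A and the method behind the power. Restate the power as about 45-60% at 1854/927 under equal 99.4% rates, before any loss from weighting. Add a range for better experimental rates, for example score power of about 76% at 0.4% failures.

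**Section 7.2.** For Endpoint A, specify a score-type (Farrington-Manning / Miettinen-Nurminen) interval for the risk difference, or a test inversion at the −0.011 null calibrated by simulation. Either must carry the IPT weights, and its size and power should be checked by simulation under weighting. Rule out a Wald or t-based interval for this endpoint. Use a profile-likelihood interval only if its slight excess (0.46% against 0.417%) is calibrated away. State whether the interval is one- or two-sided.

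**Cost.** Analysis programming, a simulation, and a less favourable stated power; no additional patients.
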